#### 9.4.5 BASELINE DESCRIPTIVE STATISTICS

Not applicable

#### 9.4.6 PLANNED INTERIM ANALYSES

See section 9.4.2. If the first dose level exceeds the MTD, the study will be suspended.

# 9.4.7 SUBGROUP ANALYSES

Not applicable

#### 9.4.8 TABULATION OF INDIVIDUAL PARTICIPANT DATA

Not applicable

#### 9.4.9 EXPLORATORY ANALYSES

Toxicity events for NE-DLI will be descriptively summarized at each dose level. Overall survival, defined from date of treatment to date of death or censored at last follow-up date, will be estimated via Kaplan-Meier method (combining patients treated at the RP2D dose level and expansion cohort patients). Other outcomes such as independence from red blood cell transfusion or platelet transfusion for 56 consecutive days or more, occurrence of AE, unexpected transplant complications will be descriptively reported via summary statistics.

# 10 SUPPORTING DOCUMENTATION AND OPERATIONAL CONSIDERATIONS

10.1 REGULATORY, ETHICAL, AND STUDY OVERSIGHT CONSIDERATIONS

#### 10.1.1 INFORMED CONSENT PROCESS

# 10.1.1.1 CONSENT/ASSENT AND OTHER INFORMATIONAL DOCUMENTS PROVIDED TO PARTICIPANTS

A study investigator, study research nurse, or clinical trial coordinator working on this study will obtain written informed consent. An explanation of the nature of study, its purpose, procedures involved, expected duration, potential risks and benefits will be provided to each participant by the investigator or the research nurse. Each participant will be informed that participation in the study is voluntary and that he may withdraw from the study at any time, and that withdrawal of consent will not affect his subsequent medical treatment. Participants will be allowed time needed to make an informed decision. Participants will be encouraged to ask questions about the study and the consent before signing the consent form. Consent forms will be filed with the Clinical Research Office and copies stored securely with the study coordinator. No patient will enter the study before his informed consent has been obtained.

#### 10.1.1.2 CONSENT PROCEDURES AND DOCUMENTATION

Informed consent is a process that is initiated prior to the individual's agreeing to participate in the study and continues throughout the individual's study participation. Consent forms will be IRB-approved and the participant will be asked to read and review the document.

The investigator will explain the research study to the participant and answer any questions that may arise. A verbal explanation will be provided in terms suited to the participant's comprehension of the purposes, procedures, and potential risks of the study and of their rights as research participants.

Participants will have the opportunity to carefully review the written consent form and ask questions prior to signing. The participants should have the opportunity to discuss the study with their family or surrogates or think about it prior to agreeing to participate. The participant will sign the informed consent document prior to any procedures being done specifically for the study.

Participants must be informed that participation is voluntary and that they may withdraw from the study at any time, without prejudice. A copy of the informed consent document will be given to the participants for their

records. The informed consent process will be conducted and documented in the source document (including the date), and the form signed, before the participant undergoes any study-specific procedures. The rights and welfare of the participants will be protected by emphasizing to them that the quality of their medical care will not be adversely affected if they decline to participate in this study.

#### 10.1.2 STUDY DISCONTINUATION AND CLOSURE

This study may be temporarily suspended or prematurely terminated if there is sufficient reasonable cause. Written notification, documenting the reason for study suspension or termination, will be provided by the suspending or terminating party to study participants, investigator, funding agency, the IND sponsor and regulatory authorities. If the study is prematurely terminated or suspended, the PI will promptly inform study participants, the IRB, and sponsor and will provide the reason(s) for the termination or suspension. Study participants will be contacted, as applicable, and be informed of changes to study visit schedule.

Circumstances that may warrant termination or suspension include, but are not limited to:

- Determination of unexpected, significant, or unacceptable risk to participants
- Demonstration of efficacy that would warrant stopping
- Insufficient compliance to protocol requirements
- Data that are not sufficiently complete and/or evaluable
- Determination that the primary endpoint has been met
- Determination of futility

Study may resume once concerns about safety, protocol compliance, and data quality are addressed, and satisfy the sponsor, IRB and/or FDA.

#### 10.1.3 FUTURE USE OF STORED SPECIMENS AND DATA

Data collected for this study will be analyzed and stored at the Moffitt Cancer Center. After the study is completed, the de-identified, archived data will be transmitted to and stored at the Moffitt Cancer Center, for use by other researchers including those outside of the study. Permission to use this data will be included in the informed consent.

These samples could be used to research the causes of myelodysplastic syndrome and/or acute myeloid leukemia, its complications and other conditions for which individuals with myelodysplastic syndromes/acute myeloid leukemia are at increased risk, and to improve treatment. The Moffitt Cancer Center will also be provided with a code-link that will allow linking the biological specimens with the phenotypic data from each participant, maintaining the blinding of the identity of the participant.

During the conduct of the study, an individual participant can choose to withdraw consent to have biological specimens stored for future research. However, withdrawal of consent with regard to biosample storage may not be possible after the study is completed.

When the study is completed, access to study data and/or samples will be provided through the Moffitt Cancer Center.

#### 10.1.5 SAFETY OVERSIGHT

SAEs from this protocol will be reported concurrently to the IRB and the study sponsor. The Protocol Monitoring Committee (PMC) will review these SAEs in accordance with the protocol-specific DSMP. The data and safety plan will define dose limiting toxicities, rules for escalation of dose, and criteria for stopping the trial and defining the MTD according to rules set forth by this protocol. This trial will be continuously monitored by the PI and the research team and reviewed at bi-weekly Immunotherapy/Cell Therapy Research Group meetings. Safety and monitoring reports will be submitted to the PMC after completing each odd numbered dose level (ie, 1, 3, 5, etc.) or more frequently if requested by the PMC. A final safety and monitoring report will be submitted to the PMC within three

months of defining the MTD. This protocol will be subject to periodic internal audits based on risk or as recommended by the PMC.

#### 10.1.6 CLINICAL MONITORING

MCC's Internal Monitors will periodically monitor regulatory documents and CRFs according to the protocol specific CMP. Monitoring will include review of data for accuracy, completeness, and source verification, reporting of SAEs, and adherence to the protocol, GCP guidelines, and applicable regulatory requirements.

#### 10.1.7 QUALITY ASSURANCE AND QUALITY CONTROL

Each clinical site will perform internal quality management of study conduct, data and biological specimen collection, documentation and completion. An individualized quality management plan will be developed to describe a site's quality management.

QC procedures will be implemented beginning with the data entry system and data QC checks that will be run on the database will be generated. Any missing data or data anomalies will be communicated to the site(s) for clarification/resolution.

Following written SOPs, the monitors will verify that the clinical trial is conducted and data are generated and biological specimens are collected, documented (recorded), and reported in compliance with the protocol, ICH GCP, and applicable regulatory requirements (e.g., Good Laboratory Practices (GLP), Good Manufacturing Practices (GMP)).

The investigational site will provide direct access to all trial related sites, source data/documents, and reports for the purpose of monitoring and auditing by the sponsor, and inspection by local and regulatory authorities.

## 10.1.8 DATA HANDLING AND RECORD KEEPING

# 10.1.8.1 DATA COLLECTION AND MANAGEMENT RESPONSIBILITIES

Data will be captured in OnCore and/or Moffitt's electronic CTMS. For each subject enrolled, the electronic CRF must be completed by the assigned data manager or other authorized study staff. Clinical data will be entered directly from the source documents. Any paper forms should be typed or filled out indelible ink and must be legible. Errors should be crossed out but not obliterated, the correction inserted, and the change initialed and dated by the investigator or his/her authorized delegate. This also applies to records for those subjects who fail to complete the study. If a subject stops dosing or terminates from the study, the dates and reasons must be noted on the CRF. If a subject terminates from the study because of a DLT, thorough efforts should be made to clearly document the outcome.

Data collection is the responsibility of the clinical trial staff at the site under the supervision of the site investigator.

The investigator is responsible for ensuring the accuracy, completeness, legibility, and timeliness of the data reported.

#### 10.1.8.2 STUDY RECORDS RETENTION

Study documents should be retained for a minimum of 10 years after the last approval of a marketing application in an ICH region and until there are no pending or contemplated marketing applications in an ICH region or until at least 10 years have elapsed since the formal discontinuation of clinical development of the study intervention.

These documents should be retained for a longer period, however, if required by local regulations. No records will be destroyed without the written consent of the sponsor, if applicable. It is the responsibility of the sponsor to inform the investigator when there is no longer a need for these documents to be retained. Permission must be acquired from the State of Florida for document destruction after the 10-year minimum record-retention period described above has elapsed.

#### 10.1.9 PROTOCOL DEVIATIONS

A protocol deviation is any noncompliance with the clinical trial protocol, ICH GCP, or MOP requirements. The noncompliance may be either on the part of the participant, the investigator, or the study site staff. As a result of deviations, corrective actions are to be developed by the site and implemented promptly.

These practices are consistent with ICH GCP:

- 4.5 Compliance with Protocol, sections 4.5.1, 4.5.2, and 4.5.3
- 5.1 QA and QC, Section 5.1.1
- 5.20 Noncompliance, sections 5.20.1, and 5.20.2.

It is the responsibility of the site investigator to use continuous vigilance to identify and report deviations within 7 working days of identification of the protocol deviation, or within 7 working days of the scheduled protocol-required activity. All deviations must be addressed in study source documents. Protocol deviations must be sent to the reviewing IRB per their policies. The site investigator is responsible for knowing and adhering to the reviewing IRB requirements. Further details about the handling of protocol deviations will be included in the MOP. Deviations must be entered into the CTMS.

#### 10.1.10 PUBLICATION AND DATA SHARING POLICY

This study will be conducted in accordance with the Food and Drug Administration (FDA) publication and data sharing policies and regulations for FDA funded research:

FDA will ensure grantee and contractor compliance with planned publication access and data management requirements by requiring, as a term and condition of the grant or contract award, periodic reporting to contracting officer representatives and program officers as a part of regular grants and contract management. Extramural researchers will periodically report

- all published articles resulting from research funding and the unique FDA manuscript repository identifier associated with the article; and
- the status of data collection and preservation, including deviation from the approved data management plan.

Failure to comply with the publication access and data management requirements—including the periodic reporting requirements—may serve as grounds to terminate the contract or cancel the grant. This decision rests with the contracting or grants management officer and will be made only after a careful review of all relevant facts and circumstances, and with appropriate consultation with the program office administering the grant or contract.

Prior to funding new grant and contract awards or continuing non-competing continuation awards, FDA will confirm awardees are in compliance with the FDA Public Access Policy. FDA will not award a grant or contract until an awardee has come into compliance with the policy.

# 10.1.11 CONFLICT OF INTEREST POLICY

The independence of this study from any actual or perceived influence, such as by the pharmaceutical industry, is critical. Therefore, any actual conflict of interest of persons who have a role in the design, conduct, analysis, publication, or any aspect of this trial will be disclosed and managed. Furthermore, persons who have a perceived conflict of interest will be required to have such conflicts managed in a way that is appropriate to their participation in the design and conduct of this trial. The study leadership in conjunction with the National Cancer Institute has established policies and procedures for all study group members to disclose all conflicts of interest and will establish a mechanism for the management of all reported dualities of interest.

# 10.2 ABBREVIATIONS

MDS	Myelodysplastic syndrome
HMA	Hypomethylating Agent
sAML	Secondary acute myeloid leukemia
MTD	Maximum Tolerated Dose
IWG	International Working Group
GVHD	Graft-versus-host disease
ANC	Absolute neutrophil count
CBC	Complete blood count
CMP	Comprehensive metabolic panel
CMV	Cytomegalovirus
CXR	Chest x-ray
Diff	Differential blood count
Echo	Echocardiogram
EKG	Electrocardiogram
MUGA	Multigated acquisition (cardiac)
PCR	Polymerase chain reaction
Allo	Allogeneic
BMT	Bone marrow transplant
PD1	programmed cell death protein 1
PDL1	PD1 ligand
CTLA4	cytotoxic T lymphocyte associated protein 4
DLI	Donor lymphocyte infusion
NE-DLI	Nonengrafting DLI (CD8 depleted DLI)
AHD	Antecedent hematologic disorder
WHO	World Health Organization
RP2D	Recommended phase 2 dose
ATRA	All trans-retinoic acid
ECOG	Eastern Cooperative Oncology Group
CrCl	Creatinine clearance
IND	Investigational New Drug Application
IRB	Investigational Review Board
LVEF	Left ventricular ejection fraction
MCC	Moffitt Cancer Center
MedDRA	Medical Dictionary for Regulatory Activities
MOP	Manual of Procedures
MSDS	Material Safety Data Sheet
NIH	National Institutes of Health
NIH IC	NIH Institute & Center
OHRP	Office for Human Research Protections
PI	Principal Investigator
QA	Quality Assurance
QC	Quality Control
SAE	Serious Adverse Event
SAP	Statistical Analysis Plan
SMC	Safety Monitoring Committee
SOC	System Organ Class
SOP	Standard Operating Procedure
IBW	Ideal Body Weight

CONSORT	Consolidated Standards of Reporting Trials		
DLT	Dose Limiting Toxicity		
ORR	Overall Response Rate		
CRS	Cytokine Release Syndrome		
CRF	Case Report Forms		
FACT	Foundation for the Accreditation of Cellular Therapy		
AE	Adverse Event		
CTCAE	Common Terminology Criteria for Adverse Events		
NCI	National Cancer Institute		
НАМА	Human anti-mouse antibodies		
mAbs	Monoclonal antibodies		
UP	Unanticipated Problems		

# 10.3 PROTOCOL AMENDMENT HISTORY

Any changes to the protocol will be made in the form of an amendment and must be approved by the IRB before implementation.

The table below is intended to capture changes of IRB-approved versions of the protocol, including a description of the change and rationale. A Summary of Changes table for the current amendment is located in the Protocol Title Page.

Version	Date	Description of Change	Brief Rationale
2.0	1/25/2019	[name] formatted into MCC Template; minor editing and changes.	All Moffitt Cancer Center Clinical Trial Protocols must be in the MCC template.
2.1	2/8/2019	[name] added additional information and reviewed Version 2.0 changes.	Completed the template and reviewed for clarity.
2.2	2/11/2019	[name] addressed [name] questions and provided secondary minor edits and reformatting.	Answered [name] questions, provided consistent formatting.
3.0	2/12/2019	[name] edits	Approval of comments by [name]
3.1	2/14/2019	[name] review and final edits.	Finalizing format.
3.2	2/14/2019	[name] reviewed [name]'s formatting before resubmission to PI.	Finalize formatting

Version 10 29 March 2023

#### 12 APPENDIX

# 12.1 APPENDIX A: INTERNATIONAL PROGNOSTIC SCORING SYSTEM- REVISED OF MYELODYSPLASTIC SYNDROME(58)

**Table 1: Prognostic score variables** 

Prognostic Variable	0	0.5	1	1.5	2	3	4
Cytogenetics	Very Good		Good		Intermediate	Poor	Very Poor
BM Blast %	<=2		>2-<5%		5-10%	>10%	
Hemoglobin	=>10		8-<10	<8			
Platelets	=>100	50-<100	< 50				
ANC	=>0.8	< 0.8					

### Table 2: Cytogenetic Risk Groups

MDS Cytogenetic Scoring System

Prognostic subgroups,	Cytogenetic abnormalities
% of patients	
Very good (4% * /3% † )	-Y, del(11q)
Good (72% * /66% † )	Normal, del(5q), del(12p), del(20q), double including del(5q)
Intermediate (13% + /19% † .)	del(7q), +8, +19, i(17q), any other single or double independent clones
Poor (4% * /5% † )	-7, inv(3)/t(3q)/del(3q), double including -7/del(7q), complex: 3 abnormalities
Very poor (7% * /7% † )	Complex: > 3 abnormalities

**Table 3: Risk Categories** 

RISK CATEGORY	RISK SCORE
Very Low	≤1.5
Low	>1.5-3
Intermediate	>3-4.5
High	>4.5-6
Very High	>6

## 12.2 APPENDIX B: RESPONSE CRITERIA ACCORDING TO THE INTERNATIONAL WORKING GROUP(1)

Category	Response criteria (responses must last at least 4 wk)		
Complete remission	Bone marrow: ≤ 5% myeloblasts with normal maturation of all cell lines*		
	Persistent dysplasia will be noted*†		
	Poripheral blood±		
	Hgb ≥ 11 g/dL		
	Platelets ≥ 100 × 10°/L		
	Neutrophils $\geq 1.0 \times 10^9 L^{\frac{1}{4}}$		
	Blasts 0%		
Partial remission	All CR criteria if abnormal before treatment except:		
	Bone marrow blasts decreased by ≥ 50% over pretreatment but still > 5%		
	Cellularity and morphology not relevant		
Marrow CR†	Bone marrow: ≤ 5% myeloblasts and decrease by ≥ 50% over pretreatment+		
	Peripheral blood: if HI responses, they will be noted in addition to marrow CR+		
Stable disease	Failure to achieve at least PR, but no evidence of progression for > 8 wks		
Failure	Death during treatment or disease progression characterized by worsening of cytopenias, increase in percentage of bone		
	marrow blasts, or progression to a more advanced MDS FAB subtype than pretreatment		
Relapse after CR or PR	At least 1 of the following:		
	Return to pretreatment bone marrow blast percentage		
	Decrement of ≥ 50% from maximum remission/response levels in granulocytes or platelets		
	Reduction in Hgb concentration by ≥ 1.5 g/dL or transfusion dependence		
Cytogenetic response	Complete		
	Disappearance of the chromosomal abnormality without appearance of new ones		
	Partial		
	At least 50% reduction of the chromosomal abnormality		
Disease progression	For patients with:		
	Loss than 5% blasts: ≥ 50% increase in blasts to > 5% blasts		
	5%-10% blasts; ≥ 50% increase to > 10% blasts		
	10%-20% blasts: ≥ 50% increase to > 20% blasts		
	20%-30% blasts: ≥ 50% increase to > 30% blasts		
	Any of the following:		
	At least 50% decrement from maximum remission/response in granulocytes or platelets		
	Reduction in Hgb by ≥ 2 g/dL		
	Transfusion dependence		
Survival	Endocints:		
Service of the servic	Overall: death from any cause		
	Event free: failure or death from any cause		
	PFS: disease progression or death from MDS		
	DFS: time to relapse		
	Cause-specific death: death related to MDS		

Deletions to IWG response criteria are not shown.

To convert hemoglobin from grams per deciliter to grams per liter, multiply grams per deciliter by 10.

MDS indicates myelodysplastic syndromes; Hgb, hemoglobin; CR, complete remission; HI, hematologic improvement; PR, partial remission; FAB, French-American-British; AML, acute myeloid leukemia; PFS, progression-free survival; DFS, disease-free survival.

\*Dysplastic changes should consider the normal range of dysplastic changes (modification).41

†Modification to IWG response criteria.

‡In some circumstances, protocol therapy may require the initiation of further treatment (eg. consolidation, maintenance) before the 4-week period. Such patients can be included in the response category into which they fit at the time the therapy is started. Transient cytopenias during repeated chemotherapy courses should not be considered as interrupting durability of response, as long as they recover to the improved counts of the previous course.

## 12.3 APPENDIX C: EVALUATION AND MANAGEMENT OF CYTOKINE RELEASE SYNDROME(75)

#### Grading of Cytokine Release Syndrome

(Assess daily and any time there is a change in patient status)

CRS Parameter	Grade 1	Grade 2	Grade 3	Grade 4		
Fever	Temperature ≥ 38°C	Temperature ≥ 38°C	Temperature ≥ 38°C	Temperature ≥ 38°C		
	With either:					
Hypotension	None	Not requiring vasopressors	Requiring one vasopressor (with or without vasopressin)	Requiring multiple vasopressors (excluding vasopressin)		
		◆ And/or				
Нурохіа	None	Requiring low-flow nasal cannula	Requiring high-flow nasal cannula, facemask, nonrebreather mask, or Venturi mask	Requiring positive pressure (eg: CPAP, BiPAP, intubation and mechanical ventilation)		

Adapted from Lee DW, et al. Biol Blood Marrow Transplant. 2018 Dec 25. [Epub ahead of print]

- CRS grade is determined by the most severe event: hypotension or hypoxia not attributable to any other cause
- Organ toxicities associated with CRS may be graded according to CTCAE v5.0, but do not influence CRS grading

Terms	Definitions			
Fever	Temperature ≥ 38°C not attributable to any other cause.     In patients who have CRS then receive antipyretics or anti-cytokine therapy such as tocilizumab/steroids, fever is no longer required to grade subsequent CRS severity. In this case, CRS grading is driven by hypotension and/or hypoxia.			
Low-flow nasal cannula	Oxygen delivered at ≤ 6 liters/minute.     Low flow also includes blow-by oxygen delivery, sometimes used in pediatrics.			
High-flow nasal cannula	Oxygen delivered at >6 liters/minute.			

#### Management of Cytokine Release Syndrome

CRS Grade	Sign or Symptom	Management
Grade 1	Fever	Symptomatic management of constitutional symptoms and organ toxicities Acetaminophen and hypothermia blanket as needed for fever Assess for infection, empiric broad spectrum antibiotics IV fluids as needed Consider tocilizumab for persistent fever lasting >3 days in patients with significant comorbidities or if patient is deteriorating
Grade 2		
All Grade 2 Cardiac telemetry and pulse oximetry, consider ECHO	Hypotension Not requiring vasopressors	IV fluid bolus of NS 500-1000 mL If patient requires multiple fluids boluses assess fluid balance and consider tocilizumab. For hypotension refractory to fluid boluses: tocilizumab 8 mg/kg IV. For high risk patients consider tocilizumab + dexamethasone 10 mg IV x one  If no response, consider redosing tocilizumab 8 mg/kg IV (may be repeated every 8 h for up to 3 doses in a 24 h period) If hypotension persists after fluids boluses and 1-2 doses of tocilizumab, or if patient is not improving or deteriorating: Consider dexamethasone 10 mg IV every 6 hours. Manage as grade 3 CRS (start vasopressors, transfer to ICU and obtain ECHO) Symptomatic management of constitutional symptoms and organ toxicities
	Hypoxia (Low-flow nasal cannula → O 2 delivered at ≤ 6 L/min)	Supplemental oxygen as needed Tocilizumab 8mg/kg IV For high risk patients consider tocilizumab + dexamethasone 10 mg IV x one If hypoxia persists after above interventions; however oxygen requirement is stable, continue close monitoring. Tocilizumab may be repeated every 8 h for up to 3 doses in a 24 h period If oxygen requirement increases or patient deteriorates: Consider dexamethasone 10 mg IV every 8 hours Manage as Grade 3 CRS Symptomatic management of constitutional symptoms and organ toxicities
Grade 3	Hypotension Requiring one vasopressor +/- vasopressin	IV fluid boluses as needed, vasopressors as needed     Transfer to ICU, obtain ECHO if not performed already     Tocilizumab if not administered previously     Start dexamethasone 10 mg IV every 6 hours if not started previously.     Alternatively methylprednisolone 1 mg/kg IV every 12 hours may be used.     Symptomatic management of constitutional symptoms and organ toxicities

	Hypoxia (High-flow nasal cannula → O 2 delivered at ≥6 L/min)	Supplemental oxygen as needed     Tocilizumab if not administered previously     Start dexamethasone 10 mg IV every 6 hours if not started previously. Alternatively methylprednisolone 1 mg/kg IV every 12 hours may be used.     Symptomatic management of constitutional symptoms and organ toxicities
Grade 4  Hypotension Requiring multiple vasopressors		Vasopressors, tocilizumab and ECHO as above Consider changing corticosteroids to high dose methylprednisolone 1000mg/day IV. Symptomatic management of constitutional symptoms and organ toxicities
	Hypoxia Requiring positive pressure	Supplemental oxygen requiring positive pressure ventilations: (CPAP, BiPAP, intubation and mechanical ventilation)     Tocilizumab     Consider changing corticosteroids to high dose methylprednisolone 1000 mg/day IV.     Symptomatic management of constitutional symptoms and organ toxicities

Adapted from Neelapu S, et al. Nat Rev Clin Oncol. 2018;15:47-62, Lee DW, et al. Biol Blood Marrow Transplant. 2018 Dec 25. [Epub ahead of print]

High risk for CRS: bulky disease, co-morbidities, early onset of CRS within 3 days of infusion

Table 3. Dosing

rable of Beening	Table 5. Dosnig				
Drug	Dose	Notes			
Tocilizumab 	8 mg/kg IV over 60 minutes (total volume 100 mL) Up to three doses in 24 hours, up to 4 doses total. Doses a minimum of 8 hours apart Maximum dose of 800 mg	First line treatment for CRS May be used for treatment of ICANS if associated with concurrent grade 2 CRS			
Dexamethasone	10 mg IV every 6 hours	Continue until improvement to grade 1 or less and then consider taper			
Methylprednisolone	1 mg/kg every 12 hours	Alternative to dexamethasone			
High dose methylprednisolone	500 mg IV every 12 hours (1000 mg/day) for 3 days followed by -250 mg IV every 12 hours for 2 days, -125 mg IV every 12 hours for 2 days, -60 mg IV every 12 hours	Taper after improvement to grade 1 CRS or ICANS			

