#### 6.5.1 RESCUE MEDICINE

The study site will supply the rescue medication tocilizumab for the management of cytokine release syndrome (CRS). This rescue medicine will be obtained locally. Although the use of rescue medications is allowable at any time during the study, the use of rescue medications should follow the algorithm for treatment of CRS as described in Appendix C. The date and time of rescue medication administration as well as the name and dosage regimen of the rescue medication must be recorded.

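### Appendix C contradicts itself on repeated dexamethasone for CRS: every 8 hours for worsening grade 2 hypoxia, every 6 hours in its other four entries

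*Combined protocol and SAP*

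**What the plan says.** Section 6.5.1 (Rescue Medicine) states that "the use of rescue medications should follow the algorithm for treatment of CRS as described in Appendix C". Section 8.4.3.3.3 likewise makes Appendix C the study's source for grading CRS and for guidance on treating it.

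The management table in Appendix C is laid out by grade and, from grade 2 upward, by sign (hypotension or hypoxia). It gives repeated dexamethasone in four of its cells:

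- Grade 2 hypoxia, when the patient worsens: "Consider dexamethasone 10 mg IV every 8 hours"; with its trigger and the instruction that follows, "If oxygen requirement increases or patient deteriorates: Consider dexamethasone 10 mg IV every 8 hours Manage as Grade 3 CRS".
- Grade 2 hypotension, when it persists or the patient worsens: "Consider dexamethasone 10 mg IV every 6 hours. Manage as grade 3 CRS".
- Grade 3 hypotension: "Start dexamethasone 10 mg IV every 6 hours if not started previously".
- Grade 3 hypoxia: "Start dexamethasone 10 mg IV every 6 hours if not started previously. Alternatively methylprednisolone 1 mg/kg IV every 12 hours may be used".

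A fifth entry is the dexamethasone line of the dosing table at the end of the appendix, which reads "10 mg IV every 6 hours" and makes no exception by grade or sign. The remaining dexamethasone mentions are one-off 10 mg doses for high-risk grade 2 patients, which have no interval.

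**The concern.** A clinician at the bedside needs one answer to how often the drug is given. For worsening grade 2 hypoxia, the appendix gives one interval in the cell, another in the grade 3 rows to which that cell refers, and that second one again in the dosing table. No reason is given for the difference.

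What is at stake is consistent use of the rescue algorithm. Section 2.3.1 lists CRS among the most serious risks of the treatment, and the inconsistency falls where a patient is moving from grade 2 to grade 3 management. Two patients treated by clinicians who both follow the appendix can end up on different schedules, and one patient with both signs can be assigned to either.

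**Working it through.** The plan states no daily total to reproduce. The check sets the entries side by side and converts each interval to a daily amount.

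**Daily amount.** The inputs are the 10 mg dose and the stated intervals. Formula: 10 mg × (24 ÷ interval in hours), assuming a full 24 hours of scheduled dosing.

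- Every 8 hours: 10 × 24/8 = 10 × 3 = 30 mg per 24 h.
- Every 6 hours: 10 × 24/6 = 10 × 4 = 40 mg per 24 h.
- Difference: 10 mg per 24 h. The 8-hour schedule gives 10/40 = 25% less than the 6-hour one; equivalently, the 6-hour schedule gives 10/30 = 33% more than the 8-hour one.

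**Entries compared.**

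| Place in Appendix C | Interval | mg per 24 h | Strength of wording |
|---|---|---|---|
| Grade 2 hypoxia, worsening | 8 h | 30 | optional |
| Grade 2 hypotension, persisting or worsening | 6 h | 40 | optional |
| Grade 3 hypotension | 6 h | 40 | start, unless already started |
| Grade 3 hypoxia | 6 h | 40 | start, unless already started |
| Dosing table | 6 h | 40 | no condition |

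**Three places where the text gives no single answer.**

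1. *Within one cell.* The grade 2 hypoxia cell gives the 8-hour interval and then refers the patient to grade 3 management, where both rows give 6 hours. The grade 2 hypotension cell makes the same referral without conflict, because its interval already matches grade 3.
2. *Both signs present.* The grading table allows hypotension and hypoxia together and sets one overall grade by the more severe event. In a patient with both signs at grade 2, that rule does not choose between the rows. Deterioration is a trigger in each row, so the patient meets both, at 8 and at 6 hours. No tie-break is given.
3. *Moving to grade 3.* The grade 3 instruction is "Start dexamethasone 10 mg IV every 6 hours if not started previously". If the condition refers to the drug, a patient already on the 8-hour schedule stays on it. If it refers to the 6-hour regimen, that patient changes. The wording supports either reading, and nothing elsewhere in the appendix settles which is meant.

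**The case against.** The strongest reply is that the table is organised by sign as well as by grade, so a different interval for hypoxia could be deliberate. Tocilizumab at grade 2 already differs by sign: for hypotension it is given once fluid boluses have failed, and for hypoxia without that step. This stands as far as it goes. A difference by sign is not an error in itself, and the documents do not support a demand for one schedule per grade. It does not explain why the hypoxia cell refers to grade 3 rows with another interval, or why the dosing table omits the 8-hour schedule.

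A reader might also infer that patients at the same grade will receive different steroid exposure. The text does not establish that. Both grade 2 entries only ask the clinician to consider the drug. The grade 3 rows allow methylprednisolone instead, and high-risk grade 2 patients may get a single dose, so exposure already varies by design. The condition in the grade 3 rows can also be read as moving the patient to 6-hourly dosing.

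Another tempting inference is that the DLT count and the MTD are affected, since grade 3-4 CRS is a DLT. Appendix C grades CRS on fever, vasopressor need and oxygen need, and nothing in the documents shows that 30 against 40 mg per day alters progression to grade 3. Nor do they say anything about an effect of this steroid difference on the infused T cells.

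Finally, a reader might think that steroid use goes unrecorded. Section 6.5.1 already requires the date, time, name and dosage regimen of rescue medication. It names only tocilizumab as supplied by the site, but its wording covers rescue medications in general. Section 8.4.6 also asks for concomitant medications and treatment in adverse experience reports.

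**Conclusion.** The contradiction holds as an internal inconsistency in an operative rescue algorithm. One of five repeated-dosing entries differs from the other four, by 10 mg per 24 hours (30 against 40 mg). It can affect patients with worsening grade 2 hypoxia for whom the clinician chooses repeated dexamethasone and follows that row, and it is sharpest for those who have both signs or go on to grade 3.

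The conclusion rests on two assumptions. The first is that the 8-hour figure is what the original page says: the point turns on one digit in a table whose text is garbled nearby in the copy read. The second is that no document outside the protocol resolves the difference. That four entries agree does not show which interval is correct, and no view is taken on that. The point changes no sample size, error rate, CRS grading rule or DLT definition.

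**What to change.** 1. Check the grade 2 hypoxia entry against the original page of Appendix C.
2. If the 8-hour figure is confirmed, reconcile that row with its own referral to grade 3 management, with the other rows and with the dosing table. If the difference by sign is intended, say so in the table, add the schedule to the dosing table, and say which row applies to a patient with both signs.
3. Reword the condition in the grade 3 rows so that it states what applies to a patient already on the other schedule.

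The clinical team decides which schedule is right. The cost is appendix wording only, with no change to design, sample size or analysis.
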